# 17. LIST OF FINAL REPORT TABLES, LISTINGS AND FIGURES

For the complete list of tables, listings and figures please refer to the Table of Contents (TOC) stored in Enterprise/eTMF Repository/V59\_75/Cluster Documents/Statistical analysis/Statistical analysis Plan.

# 18. LAYOUT SPECIFICATIONS FOR TABLES, LISTINGS AND FIGURES

All TFL is to include the following header:

Novartis Vaccines Vaccine: MenACWY

Final Report: Study V59 75 Four Doses in Children 2 Month of Age

In all tables, listings and figures, vaccine groups will be labeled as "MenACWY".

For the mock-up catalogue to be used during programming, please refer to the document stored in Home/analysis/V59/V59\_75/final/prod/docs within the SAS Drug Development (SDD) server.

Since all TLFs will be produced using SAS®, the output actually generated may slightly differ from the mock-ups presented in the study specific Mock-up catalogue.

#### 1. BACKGROUND AND RATIONALE

The purpose/aim of this Phase IV multicenter open label study is to evaluate the safety and the persistence of the antibody response among children who received 4 doses of the MenACWY conjugate vaccine at 2, 4, 6 and 12 months of age in the republic of South Korea, as a post marketing commitment.

MenACWY (Menveo®) has been approved for use in South Korea, from 2 years up to 55 years of age. The indication was extended in May 2014 to infants 2 months of age to 55 years, and as post commitment of indication change, the Regulatory Authorities of the Republic of South Korea (MFDS) have requested data on immunogenicity persistence in the Korean children population who received 4 doses of Menveo® at 2, 4, 6 and 12 months of age.

For further details please refer to section 1.0 of the protocol.

# **Reason for Analysis Plan update:**

In protocol V3, the Time and Events table has been updated to be aligned with the protocol text that clinical visits need to be planned based on the previous visit and not based on a fixed time schedule. For this reason, a line with 'Days post Injection' has been added' to the table

In protocol version 2, updates were made related to the change of the sponsor from Novartis vaccines to GlaxoSmithKline. This update did not trigger a SAP amendment. The sponsor name is updated in the current version of the SAP together with updates from protocol V3.

Some corrections were made in the protocol that does not affect the Statistical Analysis Plan.

Table 1-1 History of Protocol and SAP versions

Protocol Version	SAP version	Reason for SAP update/not update
V1, 10DEC 14	V1, 24JUN 15	Initial version
V2, 08 AUG 15		Update of protocol not triggering a SAP update
V3, 26 FEB 16	V2, 09 FEB 15	Time and Events Table updated

#### 2. OBJECTIVES

# 2.1 Primary Objective(s)

# **Primary Safety Objective(s)**

To assess the safety and tolerability of MenACWY administered at 2, 4, 6 and 12 months of age.

# **Primary Immunogenicity Objective(s)**

- 1. To evaluate the persistence of the antibody response against *N. meningitidis* serogroups A, C, W and Y at approximately 1 year after completion of a 4-dose infant vaccination series (2, 4, 6 and 12 months of age) of MenACWY vaccine as measured by hSBA titers ≥8.
- 2. To evaluate the persistence of the antibody response against *N. meningitidis* serogroups A, C, W and Y at approximately 1 year after completion of a 4-dose infant vaccination series (2, 4, 6 and 12 months of age) of MenACWY vaccine as measured by rSBA titers ≥8 and ≥128.

# 2.2 Secondary Objective(s)

- 1. To describe hSBA titers ≥8 and hSBA GMTs against *N. meningitidis* serogroups A, C, W and Y 1 month after a full vaccination series at 2, 4, 6 and 12 months of age.
- 2. To describe rSBA titers ≥8 and ≥128 and rSBA GMTs against *N. meningitidis* serogroups A, C, W and Y 1 month after a full vaccination series at 2, 4, 6 and 12 months of age
- 3. To evaluate the persistence of the antibody response against *N. meningitidis* serogroups A, C, W and Y at approximately 1 year after completion of a 4-dose infant vaccination series (2, 4, 6 and 12 months of age) of MenACWY vaccine as measured by hSBA GMTs and rSBA GMTs.

#### 3. STUDY DESIGN

This is a Phase IV multicenter open label study planned at 6 sites. The study design has 6 clinical visits. At the first 4 visits the subjects will receive a dose of MenACWY vaccine and at visit 5 and 6 a blood draw will be taken. The subjects study participation is approximately 22 months. See also Table 3-1 for an overview of the clinical visits and Table 3-2 for the time and events.

Table 3-1: Overview of the study design

Number	Visit 1	Visit 2	Visit 3	Visit 4	Visit 5	Visit 6
of Subjects	2-Months	4-Months	6-Months	12-Months	13- Months	24- Months
135	Menveo®	Menveo®	Menveo®	Menveo®	Blood draw	Blood draw

For further details please refer to section 3.0 of the protocol.

Table 3-2: Time and Events Table – Treatment Period

Visit Type		Clinic Visit	Reminder Phone Call	Clinic Visit	Reminder Phone Call	Clinic Visit	Reminder Phone Call	Clinic Visit	Reminder Phone Call	Clinic Visit	Clinic Visit
Study Day		1	3	61	63	121	123	301	303	331	661
Days Post Injections			2 days post dose 1	60 days post dose 1	2 days post dose 2	60 days post dose 2	2 days post dose 3	180 days post dose 3	2 days post dose 4	30 days post dose 4	330 days post visit 5
Visit Window (Days)		n/a	-1/+1	+/-7	n/a	+/-7	-1/+1	+14	-1/+1	-7/+14	+/-60
Months of age		2		4		6		12		13	24
Visit Number		1		2		3		4		5	6
Study Event	References										
Study Treatment											
Vaccination	Section 5.2	X		X		X		X			
Screening and Safety											
Inform Consent *	Section 5.1.1	X a									
Medical History	Section 5.1.2	X									
Physical Exam	Section 5.1.2 and 5.3.1	X b		X		X		X		X	X
Exclusion/Inclusion Criteria	Section 4.0	X c		X		X		X		X	X
30 Minutes Post Injection Assessment	Section 5.2.1	X		X		X		X			
Subject Diary Dispensed/Training	Section 5.2.1	X		X		X		X			

Visit Type	Visit Type		Reminder Phone Call	Clinic Visit	Reminder Phone Call	Clinic Visit	Reminder Phone Call	Clinic Visit	Reminder Phone Call	Clinic Visit	Clinic Visit
Study Day		1	3	61	63	121	123	301	303	331	661
Days Post Injections			2 days post dose 1	60 days post dose 1	2 days post dose 2	60 days post dose 2	2 days post dose 3	180 days post dose 3	2 days post dose 4	30 days post dose 4	330 days post visit 5
Visit Window (Days)		n/a	-1/+1	+/-7	n/a	+/-7	-1/+1	+14	-1/+1	-7/+14	+/-60
Months of age		2		4		6		12		13	24
Visit Number		1		2		3		4		5	6
Study Event	References										
Subject Diary Reminder Call	Section 5.2.2		X		X		X		X		
Subject Diary Review/ Collect	Section 5.3.1			X		X		X		X	
Assess all solicited AEs	Section 7.1.1 and 7.1.3	X d		X d		X d		X d		$X^d$	
Assess SAEs	Section 7.1.4	Xe		Xe		Xe		Xe		Xe	Xe
Medically attended AEs, AEs leading to withdrawal	Section 7.1.4.1 and 7.1.3	Xe		X e		Xe		X e		Xe	Xe
Immunogenicity											
Serology blood draw	Section 3.5.									X	X

### **Notes:**

a. Confirm consent form(s) signed prior to any procedures. \* May be collected up to 5 days prior to vaccination on day 1.

- b. Physical examination must be performed by a qualified healthcare professional.
- c. Procedures to be performed prior to vaccination.
- d. Only solicited adverse event (AE) occurred during the day of each vaccination and for the following 6 days will be reported by the subject on a subject diary.
- e. SAEs, medically attended AE and AEs leading to study or vaccine withdrawal will be collected through Day 661. Please see section 7.0 for greater detail regarding methods for SAE and AEs leading to study or vaccine withdrawal collection

#### 4. RANDOMIZATION AND BLINDING

# 4.1 Method of Group Assignment and Randomization

This is a non-randomized, single-arm study. Enrolled subjects will be manually assigned a unique Subject ID. The Subject ID will be the subject's unique identification number for all CRFs and associated study documentation that will be used for duration of the study.

For further details please refer to section 5.1.4 of the protocol.

#### 4.1.1 Definition of Vaccination Errors

The list below provides some examples of potential errors that may occur during vaccination:

- Subjects got vaccinated with a vaccine different from the one assigned
- Subjects got vaccinated with the correct vaccine but containing a lower volume

Please see section 7 of this document for a complete guidance on how vaccination errors are handled in the statistical analysis.

# 4.2 Blinding and Unblinding

Not Applicable.

#### 5. SAMPLE SIZE AND POWER CONSIDERATIONS

A total of 135 subjects will be enrolled in this study. This will lead to an estimated 100 evaluable subjects after taking into account an approximately 25% drop-out rate. The sample size is based on the number of subjects requested and agreed upon with the South Korean Heath Authorities for this persistence study.

Sample size/power considerations are included in the study protocol. Technical details including statistical assumptions and software are given in a separate sample size memo authored by the study Biostatistician. In the same document, a statistical co-reviewer verified and documented the sample size/power considerations. This document was completed prior to finalization of the protocol and stored in Enterprise/eTMF Repository/V59\_75/Cluster Documents/Statistical analysis /Statistical Analysis Plan/Other.

For details please refer to section 8.5 of the protocol.

#### 6. DETERMINATION OF PROTOCOL DEVIATIONS

#### 6.1 Definition of Protocol Deviations

Clinical Study Report (CSR) reportable protocol deviations (PDs) are defined in accordance with ICH E3 as important PDs related to study inclusion or exclusion criteria, conduct of the trial, subject management or subject assessment resulting in the potential to jeopardize the safety or rights of the trial subjects or the scientific value of the trial.

All reportable PDs will be evaluated before the analysis and classified according to ICH into the following five categories:

- Subject developed withdrawal criteria during the study but was not withdrawn
  - Underlying medical condition forbidden by the protocol or which may influence immune response.
  - Subject had contraindication for a subsequent study vaccination but was vaccinated
  - Concomitant infection related to the vaccine which may influence immune response.
- Subject received wrong vaccine or incorrect dose
  - Study vaccine was not administered at all
  - Vaccine administration not according to protocol.
- Subject took an excluded concomitant medication
  - Administration of concomitant vaccine(s) forbidden in the protocol.
  - Administration of any medication forbidden by the protocol.
- Subject enrolled and did not satisfy the entry criteria
  - Subject did not meet entry criteria.
- Key study procedures missed or performed out of window
  - Subject did not comply with study vaccination schedule.
  - Subject did not provide any post-vaccination safety data.
  - Subject did not comply with blood draw schedule.
  - Serological results not available post-vaccination.
  - Obvious incoherence, abnormal serology evolution or error in data.

CSR reportable PD will lead to exclusion of the subject or part of the subject's data from at least one analysis set.

The number of subjects in any and by PD category will be summarized by center and overall and individual subject listings will be provided in an appendix.

Prior to the analysis, designated sponsor staff will develop a memo that describes the PDs that lead to exclusions from analysis sets. This memo will be signed off by at least the Biostatistician and the Cluster Physician and will be included in the trial master file (Exclusion Memo).

Prematurely terminating study participation for reasons such as withdrawal of consent or occurrence of adverse events (including death) is not considered as a PD. The missing assessments that should have otherwise been collected for that subject later in the study are also not considered as a PD.

#### **6.2** Determination of Protocol Deviations

Prior to the analysis, a set of listings will be provided to the Cluster Physician and the Clinical Trial Leader (CTL) for review according to SOP MON-11.

The listings will be programmed following the list presented in table in section 7.7, and specifically using the PD codes specified in the first column.

After the review, the Cluster Physician and the CTL will provide the Biostatistician with:

- An assessment of CSR reportable PD based on clinical data review.
- An assessment of subjects without PD (e.g., premature withdrawals due to adverse event, withdrawal of consent) who should be excluded from an analysis set.

# **6.3** Exclusions of Individual Values for Safety Analysis

Some local and systemic adverse events will be directly measured by the subject and will not be subject to a reconciliation process, even if they are biologically implausible. Therefore these implausible measurements will be removed from the analysis but included in listings. Implausible measurements are summarized in the table below:

# **Table 6.3-1:** Implausible Solicited Adverse Events

Parameter	Implausible measurements
Body temperature	$\leq 33$ °C or $\geq 42$ °C
Erythema	For subjects < 6 years: ≥ 450 mm Measurements < 0 mm
Induration	For subjects < 6 years: ≥ 250 mm Measurements < 0 mm

#### 7. ANALYSIS SETS

#### 7.1 All Enrolled Set

All screened subjects who provide informed consent and provide demographic and/or other baseline screening measurements, regardless of the subject's vaccination status in the trial, and receive a subject ID.

# 7.2 Exposed Set

All subjects in the All Enrolled Set who receive at least one study vaccination.

# 7.3 Full Analysis Set (FAS), Immunogenicity Set

All subjects in the All Enrolled Set, who receive at least one study vaccination and provide in-treatment immunogenicity, will be included in the FAS analysis sets as defined below:

- FAS hSBA Visit 6, primary objective
  - FAS population with subjects that have an evaluable hSBA Visit 6 assessment, one year after completion of a 4-dose infant vaccination series (2, 4, 6 and 12 months of age), for at least one serogroup
- FAS rSBA Visit 6, primary objective
  - FAS population with subjects that have an evaluable rSBA Visit 6 assessment, one year after completion of a 4-dose infant vaccination series (2, 4, 6 and 12 months of age), for at least one serogroup
- FAS hSBA Visit 5, secondary objective
  - FAS population with subjects that have an evaluable hSBA Visit 5 assessment, one month after completion of a 4-dose infant vaccination series (2, 4, 6 and 12 months of age), for at least one serogroup
- FAS rSBA Visit 5, secondary objective
  - FAS population with subjects that have an evaluable rSBA Visit 5 assessment, one month after completion of a 4-dose infant vaccination series (2, 4, 6 and 12 months of age), for at least one serogroup

# 7.4 Per Protocol Set (PPS), Immunogenicity Set

All subjects in the FAS Immunogenicity set (FAS hSBAVisit5, FAS rSBAVisit5, FAS hSBA Visit 6 and FAS rSBA Visit 6) who:

- Correctly receive the vaccine (i.e., receive the vaccine and at the scheduled time points).
- Have no CSR reportable protocol deviations leading to exclusion (see section 6.2) as defined prior to analysis.
- Are not excluded due to other reasons defined prior to analysis (see section 6.2).

In case of vaccination error, the subject is excluded from the PPS.

If a subject received the correct study vaccine (dose, batch) but from another ongoing study at the site then the subject should be excluded from the PPS.

Similarly to the FAS, the PPS populations will be defined as:

- PPS hSBA Visit 6, primary objective
  - PPS population with subjects that have an evaluable hSBA Visit 6 assessment, one year after completion of a 4-dose infant vaccination series (2, 4, 6 and 12 months of age), for at least one serogroup and have no CSR reportable protocol deviations at that time point
- PPS rSBA Visit 6, primary objective
  - PPS population with subjects that have an evaluable rSBA Visit 6 assessment, one year after completion of a 4-dose infant vaccination series (2, 4, 6 and 12 months of age), for at least one serogroup and have no CSR reportable protocol deviations at that time point
- PPS hSBA Visit 5, secondary objective
  - PPS population with subjects that have an evaluable hSBA Visit 5 assessment, one month after completion of a 4-dose infant vaccination series (2, 4, 6 and 12 months of age), for at least one serogroup and have no CSR reportable protocol deviations at that time point
- PPS rSBA Visit 5, secondary objective
  - PPS population with subjects that have an evaluable rSBA Visit 5 assessment, one month after completion of a 4-dose infant vaccination series (2, 4, 6 and 12 months of age), for at least one serogroup and have no CSR reportable protocol deviations at that time point

# 7.5 Safety Set

# Solicited Safety Set

The solicited adverse events safety set will be split into 4 periods of 7 days, following each vaccination (day 1-day 7, with day 1 the day of a vaccination) to collect the solicited adverse events after each vaccination separately. The Solicited Adverse Events Safety Set per vaccination consists of all subjects in the Exposed Set with any solicited adverse event data and/or indicators of solicited adverse events at:

- Visit 1 at planned day 1 (Solicited Safety Set Visit 1)
- Visit 2 at planned day 61 (Solicited Safety Set Visit 2)
- Visit 3 at planned day 121 (Solicited Safety Set Visit 3)
- Visit 4 at planned day 301 (Solicited Safety Set Visit 4)

### **Unsolicited Safety Set**

The unsolicited adverse events safety set will be split into 4 periods, following each vaccination with duration until the next vaccination or study termination. The Unsolicited Adverse Events Safety Set consists of all subjects in the Exposed Set with any unsolicited adverse event data in the period of:

- Visit 1/day 1 to visit 2/day 61 (Unsolicited Safety Set Period 1)
- Visit 2/day 61 to visit 3/day 121 (Unsolicited Safety Set Period 2)
- Visit 3/day 121 to visit 4/day 301 (Unsolicited Safety Set Period 3)
- Visit 4/day 301 to visit 6/day 661 or study termination (Unsolicited Safety Set Period 4)
- Overall

# Overall Safety Set

All subjects who are in the solicited safety set and/or in the unsolicited safety set.

Subjects providing only 30 minutes postvaccination safety data will be reported separately in a 30 minute postvaccination safety analysis and excluded from all other safety analysis.

If a subject received the correct study vaccine (dose, batch) but from another ongoing study at the site then the subject's safety data should be included in the safety analysis.

# 7.5.1 Restricted Safety Set

Not applicable.

# 7.6 Other Analysis Set

There is no additional analysis set.

# 7.7 Overview of Analysis Sets by PD Code

**Table 7.7-1:** Unsolicited Safety Sets

PD code	PD Description	Study Objective/ Period	Safety Set, Unsolicited AEs, Period 1	Safety Set, Unsolicited AEs, Period 2	Safety Set, Unsolicited AEs, Period 3	Safety Set, Unsolicited AEs, Period 4	Safety Set, Unsolicited AEs, Overall
	Exclusion code		SSU10FL	SSU11FL	SSU12FL	SSU13FL	SSUFL
100	Study vaccine not administered AT ALL	All Study	EXC	EXC	EXC	EXC	EXC
115.1	Subject did not provide any post-vaccination unsolicited safety data in period 1	Visit 1/Day 1 to Visit 2/Day 61	EXC	None	None	None	None
115.2	Subject did not provide any post-vaccination unsolicited safety data in period 2	Visit 2/Day 61 to Visit 3/Day 121	None	EXC	None	None	None
115.3	Subject did not provide any post-vaccination unsolicited safety data in period 3	Visit 3/Day 121 to Visit 4/Day 301	None	None	EXC	None	None
115.4	Subject did not provide any post-vaccination unsolicited safety data in period 4	Visit 4/Day 301 to Visit 6/Day 661 or Study End	None	None	None	EXC	None

EXC = excluded from this analysis set; None=No exclusion;

.

Table 7.7-2: Exposed, Overall and Solicited Safety Sets

	- _							
PD code	PD Description	Study Objective/ Period	All Exposed Set	Overall Safety Set	Safety Set, Solicited AEs, Period T6H*-D7	Safety Set, Solicited AEs, Period T6H*-D3	Safety Set, Solicited AEs, Period D4-D7	Safety Set, Solicited AEs, Period T30m*
	Exclusion code		EXPFL	SAFFL	SSS10FL	SSS11FL	SSS12FL	
100	Study vaccine not administered AT ALL	All Study	EXC	EXC	EXC	EXC	EXC	EXC
116.1	Subject did not provide any post-vaccination solicited safety data after vaccination 1	Day 1 through Day 7 after Vaccination 1	None	None	EXC	EXC	EXC	None
116.2	Subject did not provide any post-vaccination solicited safety data after vaccination 2	Day 1 through Day 7 after Vaccination 2	None	None	EXC	EXC	EXC	None
116.3	Subject did not provide any post-vaccination solicited safety data after vaccination 3	Day 1 through Day 7 after Vaccination 3	None	None	EXC	EXC	EXC	None
116.4	Subject did not provide any post-vaccination solicited safety data after vaccination 4	Day 1 through Day 7 after Vaccination 4	None	None	EXC	EXC	EXC	None

\* T30m and T6H=Day 1 time points of 30 min and 6 hrs respectively following vaccination; EXC = excluded from this analysis set. None=No exclusion;

**Table 7.7-3: Immunogenicity Sets** 

PD	PD Description	Study Objective/ Period	All Exposed	FAS Visit 5	FAS Visit 6	PPS Visit 5	PPS Visit 6
code	Exclusion code		EXPFL	FAS10FL	FAS11FL	PPS10FL	PPS11FL
100	Study vaccine not administered AT ALL	All Study	EXC	EXC	EXC	EXC	EXC
110.1	hSBA serological results are not available at Visit 5	Day 331	None	EXC	None	EXC	None
110.2	hSBA serological results are not available at Visit 6	Day 661	None	None	EXC	None	EXC
110.3	rSBA serological results are not available at Visit 5	Day 331	None	EXC	None	EXC	None
110.4	rSBA serological results are not available at Visit 6	Day 661	None	None	EXC	None	EXC
112.1	Obvious deviation from Laboratory Manual or error in laboratory data at Visit 5	Day 331	None	None	None	EXC	None
112.2	Obvious deviation from Laboratory Manual or error in laboratory data at Visit 6	Day 661	None	None	None	None	EXC
140	Vaccination not according to protocol	Day 1 through Day 301	None	None	None	EXC	EXC
140.2	Administration of expired vaccine	Day 1 through Day 301	None	None	None	EXC	EXC
140.3	Administration of lower volume of the study vaccine	Day 1 through Day 301	None	None	None	EXC	EXC
140.4	Incomplete vaccination series	Day 1 through Day 301	None	None	None	EXC	EXC

PD	PD Description	Study Objective/ Period	All Exposed	FAS Visit 5	FAS Visit 6	PPS Visit 5	PPS Visit 6
code	Exclusion code		EXPFL	FAS10FL	FAS11FL	PPS10FL	PPS11FL
150.1	Administration of forbidden vaccine	Before Visit 5 (Day 331)	None	None	None	EXC	EXC
150.2	Administration of forbidden vaccine	Before Visit 6 (Day 661) but After Visit 5 (Day 331)	None	None	None	None	EXC
200	Subject did not meet entry criteria	Day 1	None	None	None	EXC	EXC
220	Subject had contraindication for a subsequent study vaccination but was vaccinated	All Study	None	None	None	EXC	EXC
230.1	Administration of forbidden medication	Before Visit 5 (Day 331)	None	None	None	EXC	EXC
230.2	Administration of forbidden medication	Before Visit 6 (Day 661) but after Visit 5 (Day 331)	None	None	None	None	EXC
240	Underlying medical condition forbidden by the protocol	All Study	None	None	None	EXC	EXC
250.1	Concomitant infection related to the vaccine which may influence immune response	Before Visit 5 (Day 331)	None	None	None	EXC	EXC
250.2	Concomitant infection related to the vaccine which may influence immune response	Before Visit 6 (Day 661) but After Visit 5 (Day 331)	None	None	None	None	EXC

PD code	PD Description	Study Objective/ Period	All Exposed	FAS Visit 5	FAS Visit 6	PPS Visit 5	PPS Visit 6
	Exclusion code		EXPFL	FAS10FL	FAS11FL	PPS10FL	PPS11FL
260.2	Visit 2 vaccination performed out of planned visit window	Visit 2 (Day 61)	None	None	None	EXC	EXC
260.3	Visit 3 vaccination performed out of planned visit window	Visit 3 (Day 121)	None	None	None	EXC	EXC
260.4	Visit 4 vaccination performed out of planned visit window	Visit 4 (Day 301)	None	None	None	EXC	EXC
270.1	Visit 5 blood draw performed out of planned visit window	Visit 5 (Day 331)	None	None	None	EXC	None
270.2	Visit 6 blood draw performed out of planned visit window	Visit 6 (Day 661)	None	None	None	None	EXC

FAS = Full Analysis Set; PPS=Per Protocol Set; EXC = excluded from this analysis set; None=No exclusion;

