#### 1.2 Rationale

Novartis MenACWY (Menveo®) has been approved for use in people 2 months through 55 years of age in the United State and in people of 2 years and above in Europe and other countries, including the Republic of South Korea. In South Korea, the indication was extended in May 2014 to infants 2 months of age to 55 years, and as post commitment of indication change, the Regulatory Authorities of the Republic of South Korea, (MFDS) have requested data on immunogenicity persistence in the Korean children who received 4 doses of Menveo® at 2-4-6-12 months of age.

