#### 4.2 Exclusion Criteria

Each subject must not have/have been:

- 1. previously received any meningococcal A, C, W and Y vaccines.
- 2. previous confirmed or suspected disease caused by *N. meningitidis* or who have had household contact with and/or intimate exposure to an individual with laboratory confirmed *N. meningitidis* infection at any time since birth.
- 3. progressive, unstable or uncontrolled clinical conditions.
- 4. a history of anaphylactic shock, asthma, urticaria or other allergic reaction after previous vaccinations or known hypersensitivity to any vaccine component, such as latex allergy.
- 5. experienced significant acute or chronic infection within the previous 7 days or have experienced fever (temperature  $\geq 38.0^{\circ}$ C [100.4°F]) within the previous 3 days.
- 6. any confirmed or suspected immunosuppressive or immunodeficient condition, based on medical history and physical examination.
- 7. received treatment with systemic administration corticosteroids (PO/IV/IM) for more than 14 consecutive days from birth.

- 8. ever received blood, blood products and/or plasma derivatives or any parenteral immunoglobulin preparation (including Hepatitis B immune globulin) at anytime since birth and for the full length of the study.
- 9. any bleeding disorder which is considered as a contraindication to intramuscular injection or blood draw.
- 10. any condition which, in the opinion of the investigator, might interfere with the results of the study or pose additional risk to the subject due to participation in the study.
- 11. received or are planning to receive any investigational or non-registered medicinal product from birth and throughout the study.
- 12. received oral or parenteral antibiotic treatment in the 3 days prior to the scheduled blood draw (topical antibiotics are acceptable, including antibiotic eye drops).
- 13. relatives of site research staff working on this study.

Prior to receipt of study vaccination, subjects must be evaluated to confirm that they are eligible for subsequent vaccination. At subsequent vaccinations, if subjects meet any of the original exclusion criteria listed above (with exception exclusion criteria 1, previous received the study vaccine), they should not receive additional vaccinations.

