#### 6.5 Prior and Concomitant Medications and Vaccines

All medications, vaccines and blood products taken or received by the subject within 60 days prior to the start of the study are to be recorded on the Prior and Concomitant Medications and Blood Products CRF.

In addition, the following are considered prior medications for this protocol: all medication/vaccines described in the inclusion and exclusion criteria of this protocol including:

- 1. Subjects treated with systemic administration corticosteroids (PO/IV/IM) for more than 14 consecutive days from birth.
- 2. Subjects who received oral or parenteral antibiotic treatment in the 3 days prior to the scheduled blood draw

The use of antipyretics and/or analgesic medications within 24 hours prior to vaccination must be identified and the reason for their use (prophylaxis versus treatment) must be described in the source document and Concomitant Medications CRF.

Medications taken for prophylaxis are those intended to prevent the onset of symptoms. Medications taken for treatment are intended to reduce or eliminate the presence of symptoms that are present.

Concomitant medications taken-by/administered to the subject to treat any medically-attended AE and SAE and all vaccines at and after enrolment and must be documented on the Concomitant Medications /CRF.

When recording concomitant medications/vaccines, they should be checked against the study entry and continuation criteria in section 4.0, Selection of Study Population to ensure that the subject should be enrolled/continue in the study.

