## 8.4.2.3.2 Analysis Sets

The primary immunogenicity objective will be run with the FAS population, however the analyses will also be run with the PPS population for sensitivity reason.

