### 8.2.2 Immunogenicity Data

Missing immunogenicity values are considered MCAR and therefore will not contain information that impact the result of the analysis (i.e., not informative). Imputation methods will therefore not be used. The primary objectives will be analyzed using the FAS as the primary population and the PPS for sensitivity.

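### A Visit 6 titre drawn after a non-study meningococcal vaccine stays in the primary Full Analysis Set and counts as persistence, and the trigger for the forbidden-vaccine codes is not defined

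*SAP*

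**What the plan says.** SAP Version 2, section 7.7, Table 7.7-3, gives codes 150.1 and 150.2 the description "Administration of forbidden vaccine". Code 150.1 applies before Visit 5, and 150.2 applies after Visit 5 but before Visit 6. Under FAS Visit 5 and FAS Visit 6 both codes read None. Under PPS Visit 6 both read EXC, and under PPS Visit 5 only 150.1 does.

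SAP section 8.2.2 states: "The primary objectives will be analyzed using the FAS as the primary population and the PPS for sensitivity". Protocol section 8.4.2.3.2 agrees: "The primary immunogenicity objective will be run with the FAS population, however the analyses will also be run with the PPS population for sensitivity reason". SAP section 7.3 defines the primary set for the human-complement assay as "FAS population with subjects that have an evaluable hSBA Visit 6 assessment", and the rabbit-complement set is parallel. Apart from at least one study dose and a result for at least one serogroup, nothing further is required. Intercurrent vaccination is not mentioned.

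For the meaning of the codes, SAP section 6.1 points back to the protocol: "Administration of concomitant vaccine(s) forbidden in the protocol". In protocol section 4.2, criterion 1 concerns earlier receipt of meningococcal A, C, W and Y vaccines, and criterion 11 bars investigational or non-registered products for the whole study. When eligibility is re-checked before later doses, criterion 1 is set aside in these words: "with exception exclusion criteria 1, previous received the study vaccine". Protocol section 6.5 requires "all vaccines at and after enrolment" to be documented.

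**The concern.** The primary question is how much bactericidal antibody remains about a year after the four study doses. A serum taken after another vaccine containing A, C, W or Y antigen answers a different question, because it measures a response to that vaccine. Such a serum can only raise the percentage at or above a threshold. It also tends to raise the Visit 6 GMT and, if the vaccine came after Visit 5, the Visit 6 to Visit 5 ratio. In a single-arm study no comparison group shares and cancels the effect, and a confidence interval does not reflect it.

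The opportunity exists. Protocol section 1.2 says of South Korea that "the indication was extended in May 2014 to infants 2 months of age to 55 years", so a licensed product is available to these children, and Visits 5 and 6 are planned 330 days apart (Day 331 to Day 661).

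**Working it through.** **Inputs from the documents.** 135 enrolled, 25% drop-out, about 100 evaluable, and the interval table at N = 100 (protocol section 8.5). Two-sided 95% Clopper-Pearson intervals (protocol section 8.4.2.3.3). Code assignments (SAP Table 7.7-3). No statistical test (SAP section 11.2).

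**Assumed inputs.** The number k of boosted children per 100; the true percentage p among the others; every boosted child reaches the threshold; and, for the GMT, a fold rise f.

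**1. The plan's own figures.** 135 × 0.75 = 101.25, and 100 / 0.75 = 133.3, rounded up to 134. Both agree with the plan. The table in section 8.5 is reproduced by p ± 1.96 × √(p(1−p)/100):
- 50%: 40.2 to 59.8
- 60%: 50.4 to 69.6
- 70%: 61.0 to 79.0
- 80%: 72.2 to 87.8
- 90%: 84.1 to 95.9

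The half-widths are therefore about 6 to 10 points. These serve as the yardstick below.

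**2. One child followed through the plan.** A child completes four study doses, receives a licensed non-study meningococcal vaccine after Visit 5, and gives blood at Visit 6.
- FAS Visit 6: the child has a dose and a result, and code 150.2 reads None. The child is included with the titre as measured.
- PPS Visit 6: excluded if the vaccine is judged forbidden.
- Primary result: the FAS.

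**3. Is that vaccine forbidden?**
- Criterion 1 looks back from enrolment. The wording that exempts it at later doses mentions only the study vaccine, so it is unclear whether a non-study meningococcal vaccine is still caught.
- Criterion 11 does not reach a licensed product.
- The eligibility check is scheduled at Visits 5 and 6, but the only consequence stated in section 4.2 is that no further study dose is given, and none remains after Visit 4.
- Section 3.8 foresees withdrawal for an excluded vaccination without saying which vaccinations those are.
- The protocol amendments are available as descriptions of changes. None of those shown adds a list.

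**4. Size for the percentages.** With k of 100 boosted, the FAS percentage is [(100−k)p + k]/100. The shift against p is k(1−p) percentage points.

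| True p | k = 1 | k = 5 | k = 10 |
|---|---|---|---|
| 50% | 0.5 | 2.5 | 5.0 |
| 60% | 0.4 | 2.0 | 4.0 |
| 70% | 0.3 | 1.5 | 3.0 |
| 80% | 0.2 | 1.0 | 2.0 |
| 90% | 0.1 | 0.5 | 1.0 |

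Example at p = 70% and k = 10: without the boosted sera, 63/90 = 70% (Clopper-Pearson 59.4 to 79.2). With them, 73/100 = 73% (63.2 to 81.4).

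**5. Size for the GMT.** The mean log titre rises by (k/100) × log10(f), so the GMT is multiplied by 10 to that power. For f = 10 and f = 50 the factor is 1.12 and 1.22 with k = 5, and 1.26 and 1.48 with k = 10. The GMR rises by the same factor if the vaccine was given after Visit 5 and all 100 children have both samples.

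**The case against.** The strongest reply is that the plan follows a consistent convention. Forbidden medication, underlying conditions, concomitant infection and missed windows are also kept in the FAS and removed from the PPS, and both documents pre-specify a PPS analysis of the primary objective. Protocol section 6.5 has concomitant vaccines checked against the entry and continuation criteria. Section 3.8 allows withdrawal, so an affected child may never reach Visit 6. SAP sections 6.1 and 6.2 require review of deviations and a signed exclusion memo before analysis. No frequency of off-study vaccination is given, licensure is not uptake, and these children already receive the licensed four-dose infant series within the study. With no test and no success criterion, no formal decision can change.

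Most of this stands, and it limits the size of the point. It does not remove it. The PPS at Visit 6 also drops children for dose and blood-draw windows, low volume, entry criteria and medication, so a difference between the sets could not be attributed to boosting, and the absence of a difference could hide it. Section 3.8 also says that children with deviations may in general remain in the study.

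Three stronger readings are tempting and go too far.
- A reader might infer that the protocol names no forbidden vaccine. Criterion 1 names meningococcal A, C, W and Y vaccines, and criterion 11 covers non-registered ones.
- A reader might infer that criterion 1 is switched off after enrolment. The exemption's wording mentions only the study vaccine, which protocol section 6.1 ties to supply by the sponsor, so an off-study product may still be caught. The text is ambiguous.
- A reader might infer that even the PPS would keep such a child. SAP section 7.4 also allows exclusion for other reasons fixed before analysis, so the outcome depends on judgement and retention is not automatic.

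**Conclusion.** The point holds in a limited form. Followed as written, the primary analysis counts a Visit 6 titre drawn after a non-study A, C, W or Y vaccine as persistence of the study series. The trigger for codes 150.1 and 150.2 with respect to a licensed meningococcal vaccine is left to judgement before analysis.

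Over the range of percentages in the planning table the effect is at most half a point per affected child per 100. Even ten children would move the result by 1 to 5 points, less than the interval half-width at the same percentage. The number affected is purely an assumption and may be zero. The change is still worth making because the error runs in one direction only, towards better persistence, and because the affected children can be identified from data already collected.

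**What to change.** In SAP section 7.7, state that codes 150.1 and 150.2 include any non-study vaccine containing meningococcal A, C, W or Y antigen. This must be in addition to vaccines the protocol already bars, such as non-registered products, so that the codes are widened and not narrowed.

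Treat serology drawn after receipt of such a meningococcal vaccine as not evaluable for the primary persistence analysis, in both FAS and PPS, and for the Visit 6 GMT and the GMR. Neither document says what makes a result evaluable, so the rule can be placed in SAP section 7.3. Report the FAS with those sera included as a sensitivity analysis. At minimum, pre-specify the reverse: an FAS analysis without them. The number of affected children should be reported either way.

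This is a rule for analysis and does not decide what a child may receive. Criterion 1, its exemption, and the references to excluded or forbidden vaccines should be reconciled by the sponsor.

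The cost is slightly fewer evaluable sera and a small departure from the keep-all FAS convention in protocol section 8.3.4. No new data are needed.
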